### 9.2. General Statistical Considerations

Statistical analysis of this study will be the responsibility of Lilly.

Continuous data will be summarized in terms of the mean, standard deviation, minimum, maximum, median, and number of observations. Categorical data will be summarized as frequency counts and percentages.

Any change to the data analysis methods described in the protocol will require an amendment ONLY if it changes a principal feature of the protocol. Any other change to the data analysis methods described in the protocol, and the justification for making the change, will be described in the clinical study report (CSR). Additional exploratory analyses of the data will be conducted as deemed appropriate.

Complete details of the planned analyses will be documented in the SAP.

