6.1.1. General Considerations for Analyses during the Blinded Treatment Dosing Period (Period 2)

Comparisons between each ixekizumab regimen (80 mg Q2W or 80 mg Q4W) and placebo, as well as comparisons between adalimumab and placebo, will be performed for all analyses in Period 2.

Period 2 starts at the first injection of study treatment at Week 0 (Visit 2) and ends prior to the first injection of study treatment at Week 16 (Visit 8) or the ETV (between Weeks 0 and 16).

Baseline will be defined as the last available value before the first injection for efficacy, health outcome, and safety analyses. In most cases, this will be the measure recorded at Week 0 (Visit 2). For efficacy measures, if the patient does not take any injection, the last available value on or prior to randomization date will be used. Change from baseline will be calculated as the visit value of interest minus the baseline value. For safety analyses using a baseline period, the baseline period is defined as the time from Visit 1 to the date/time of the first injection.

The randomization to treatment groups is stratified by country and baseline CRP status (nonelevated versus elevated) as described in Section 5.2. The countries will be categorized into geographic regions for analysis. Geographic regions are defined in Section 6.2. Unless otherwise specified, the statistical analysis models will adjust for geographic region and baseline CRP status.

Unless otherwise specified, treatment groups of ixekizumab 80 mg Q2W and Q4W will be analyzed without regard to starting dose.

The primary analysis method for treatment comparisons of categorical efficacy and health outcome variables at specific time points will be made using a logistic regression analysis with treatment, geographic region (Europe and non-Europe), and baseline CRP status in the model using PROC Logistic with a Wald test. The odds ratio and 95% CIs will be reported; treatment difference and 95% CI will also be reported. Secondary analysis will be conducted using a Fisher's exact test. In the case when logistic regression model does not produce statistical results due to sparse data, Fisher's exact test will be used.

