As a secondary analysis for the primary and major secondary categorical efficacy measures, a categorical, pseudo-likelihood based mixed-effects model of repeated measures (categorical MMRM) estimating the percentage of patients achieving response across postbaseline visits may be used. The model will include treatment, geographic region, baseline CRP status, visit, and treatment-by-visit as fixed factors. The binomial distribution and the logit link will be used. The restricted maximum likelihood (REML) will be used. An unstructured covariance matrix will be used to model the within-patient variance-covariance errors. The Kenward-Roger approximation will be used to estimate the denominator degrees of freedom. The Newton-Raphson with ridging optimization technique will be used to aid with convergence. The probability of response, the corresponding 2-sided 95% CI, and the p-value for treatment comparisons at Week 16 (Visit 8) and all other postbaseline visits will be reported.

If the unstructured covariance matrix results in a lack of convergence, the heterogeneous Toeplitz covariance structure, followed by the heterogeneous autoregressive covariance structure, followed by the compound symmetry will be used. This order is specified according to a decreasing number of covariance parameters in the structure. The sandwich estimator (Diggle et al. 1994) for the covariance estimation will be used by specifying the EMPIRICAL option in SAS PROC MIXED. When sandwich estimation is used, the Kenward-Roger approximation for denominator degrees of freedom cannot be used. Instead, DDFM= BETWITHIN option will be used to estimate denominator degrees of freedom.

The primary analyses for continuous efficacy and health outcome variables will be made using MMRM. The primary analyses for MRI endpoints will be made using analysis of covariance (ANCOVA). A secondary analysis for continuous efficacy and health outcome variables will be made using ANCOVA.

When the MMRM is used, the model will include treatment, geographic region, baseline CRP status, baseline value, visit, baseline value-by-visit, and treatment-by-visit interaction as fixed factors (except for the analysis of CRP, see paragraph below). The covariance structure to model

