6.5. Multiple Comparisons/Multiplicity

A multiple testing strategy for the primary and major secondary objectives will be implemented to control the family-wise type I error rate at a 2-sided α level of 0.05. The primary outcome will be tested by using the primary analysis method, logistic regression analysis with treatment, geographic region, and baseline CRP status in the model, with NRI missing data imputation approach.

A graphical multiple testing procedure (Bretz et al. 2011) will be used (Figure RHBV.6.1). The graphical approach is a closed testing procedure; hence, it strongly controls the family-wise error rate (Alosh et al. 2014). The following is a list of primary and major secondary outcomes to be tested for both ixekizumab 80 mg Q2W and Q4W regimen at Week 16:

- Primary - proportion of patients achieving an ASAS40 response [ASAS40]
- Secondary 1 - proportion of patients achieving an ASAS20 response [ASAS20]
- Secondary 2 - change from baseline in ASDAS score [ASDAS CFB]
- Secondary 3 - proportion of patients achieving BASDAI50 [BASDAI50]
- Secondary 4 - change from baseline in BASFI [BASFI CFB]
- Secondary 5 - proportion of patients achieving ASDAS inactive disease [ASDAS IN]
- Secondary 6 - change from baseline in MRI of the spine [MRI spine SPARCC CFB]
- Secondary 7 - change from baseline in SF-36 PCS score [SF-36 PCS CFB]
- Secondary 8 - change from baseline in ASAS-HI [ASAS-HI CFB].

The 8 secondary outcomes are grouped into 2 tiers ([Figure RHBV.6.1](#), [Figure RHBV.6.2](#), and [Figure RHBV.6.3](#)) based on statistical significance observed in historical axSpA studies as well as clinical and commercial relevance.

[Figure RHBV.6.1](#) shows the graphical testing scheme with initial α allocation and weights, and [Figure RHBV.6.2](#) and [Figure RHBV.6.3](#) show the graphical testing schemes used within the Tier 1 and Tier 2 groups of endpoints respectively. The testing steps are outlined below:

[figure not shown]
Step 1: The primary outcome of ASAS40 will be tested for ixekizumab 80 mg Q2W vs. placebo at a two-sided $\alpha=0.05$. If the null hypothesis is not rejected, no further testing is conducted as the α for that test is considered ‘spent’ and cannot be passed to other endpoints. If the null hypothesis is rejected, then move to Step 2.

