Ankylosing Spondylitis Disease Activity Score (ASDAS)	The ASDAS is a composite index to assess disease activity in AS (Machado et al. 2011a, 2011b; Zochling 2011). The parameters used for the ASDAS (with CRP as acute phase reactant): 1) Total back pain (BASDAI Q2) 2) Patient global 3) Peripheral pain/swelling	ASDAS _{crp}	ASDAS _{crp} (Sieper et al. 2009): $0.121 \times \text{total back pain} + 0.110 \times \text{patient global} + 0.073 \times \text{peripheral pain/swelling} + 0.058 \times \text{duration of morning stiffness} + 0.579 \times \text{Ln}(\text{CRP}+1)$ (Machado et al. 2015). C-reactive protein is in mg/liter, the range of other variables is from 0 to 10; Ln represents the natural logarithm.	Missing if any of the components is missing. If CRP <2 mg/L or below the limit of detection, then use 2 mg/L in the calculation (Machado et al. 2015).
		ASDAS _{crp} change from baseline - major secondary	Calculated as: observed ASDAS – baseline ASDAS	Missing if baseline or observed value is missing

Measure	Description	Variable	Derivation / Comment	Imputation Approach if with Missing Components
	(BASDAI Q3) 4) Duration of morning stiffness (BASDAI Q6) 5) CRP in mg/L	outcome		
		ASDAS Disease Activity States	Four (4) disease activity states have been defined by ASAS consensus (Machado et al. 2011c, Machado 2018): 
 • ASDAS <1.3 defines inactive disease • $1.3 \leq \text{ASDAS} < 2.1$ defines low disease activity • $2.1 \leq \text{ASDAS} \leq 3.5$ defines high disease activity • ASDAS >3.5 defines very high disease activity. 	Set the disease activity state to worst state (ie, very high) if observed ASDAS score is missing
		ASDAS<2.1	Defined as ASDAS <2.1 (low or inactive disease activity)	
		Clinical important improvement	Defined as at least 1.1 unit change in ASDAS from baseline	Missing if baseline or observed ASDAS score is missing
		Major improvement	Defined as at least 2.0 unit change in ASDAS from baseline or reached the minimum of ASDAS score (0.6361) at postbaseline visit	

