ASDAS	ASDAS Inactive Disease– Major Secondary	Logistic regression analysis with NRI	ITT Population	IXE80Q2W & IXE80Q4W vs. placebo at Week 16	Major secondary efficacy analysis is logistic regression analysis with NRI for ITT Population comparing IXE80Q2W & IXE80Q4W vs. placebo at Week 16 (Section 6.10.2).
		Logistic regression analysis with NRI	ITT Population	IXE80Q2W & IXE80Q4W vs. placebo at all other postbaseline visits in Period 2	Other secondary efficacy analyses (Section 6.10.4).
		Categorical MMRM	ITT Population	IXE80Q2W & IXE80Q4W vs. placebo at Week 16 and all other postbaseline visits in Period 2	Other secondary efficacy analyses (Section 6.10.4).
		Fisher’s exact test with NRI	ITT Population	IXE80Q2W & IXE80Q4W vs. placebo at Week 16 and all other postbaseline visits in Period 2	Other secondary efficacy analyses (Section 6.10.4).
		KM analysis of time to first ASDAS inactive disease response	ITT Population	IXE80Q2W & IXE80Q4W vs. placebo during Period 2	Other secondary efficacy analyses (Section 6.10.4).
		Subgroup analyses	ITT Population	IXE80Q2W & IXE80Q4W vs. placebo at Week 16	Subgroup analysis (Section 6.14.1)
		Descriptive statistics of ASDAS inactive disease response rate	Extended Treatment Period Population	No treatment group comparisons during Period 3	Other secondary efficacy analyses (Section 6.10.4).

Measure	Variable	Analysis Method (Sections 6.1, 6.3)	Population (Section 6.1.5)	Comparison/Time Point	Analysis Type
		Descriptive statistics of ASDAS inactive disease response rate	ITT Population Who are Initially Randomized to Ixekizumab	No treatment group comparisons during Combined Periods 2 and 3	Other secondary efficacy analyses (Section 6.10.4)
ASDAS	ASDAS <2.1	Logistic regression analysis with NRI	ITT Population	IXE80Q2W & IXE80Q4W vs. placebo at Week 16	This is an ad hoc analysis post interim 1 DBL, logistic regression analysis with NRI for ITT Population comparing IXE80Q2W & IXE80Q4W vs. placebo at Week 16.
		Descriptive statistics of ASDAS <2.1 response rate	Extended Treatment Period Population	No treatment group comparisons during Period 3	Other secondary efficacy analyses (Section 6.10.4)
		Descriptive statistics of ASDAS <2.1 response rate	ITT Population Who are Initially Randomized to Ixekizumab	No treatment group comparisons during Combined Periods 2 and 3	Other secondary efficacy analyses (Section 6.10.4)

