6.14. Subgroup Analyses

6.14.1. Efficacy Subgroup Analyses

Subgroup analysis will be conducted for the primary endpoints of proportion of patients achieving an ASAS40 response at Week 16 (NRI) using the ITT Population for the Period 2. The major secondary efficacy endpoints, the proportion of patients achieving ASAS20 (NRI) and ASDAS inactive disease (NRI) at Week 16, will also be conducted.

For categorical response variables (ASAS20, ASAS40, and ASDAS inactive disease), a logistic regression analysis with treatment, subgroup, and treatment-by-subgroup interaction as factors will be used. The treatment-by-subgroup interaction will be tested at the 10% significance level. Treatment group differences will be evaluated within each subgroup using the Fisher's exact test, regardless of whether the interaction is statistically significant. If any group within the subgroup (for example, yes, no) is <10% of the total population, only descriptive statistics will be provided for that subgroup (that is, no inferential testing).

Forest plots may be created to illustrate the treatment differences with 95% CIs between each of the ixekizumab treatment groups and placebo group, by each subgroup category.

The following subgroups will be analyzed:

- Patient Demographics Subgroups:
 - Sex
 - Age category: <40 years, ≥40 years
 - Age category: <50 years, ≥50 years
 - Age category: <65 years, ≥65 years
 - Weight: <70 kg, ≥70 kg
 - BMI: underweight (<18.5 kg/m²); normal (≥18.5 and <25 kg/m²); overweight (≥25 and <30 kg/m²); obese (≥30 and <40 kg/m²); or extreme obese (≥40 kg/m²)
 - Ethnicity: Hispanic/Latino, Non-Hispanic/Non-Latino
 - Race: American Indian/Alaska Native, Asian, Black/African American, Native Hawaiian or other Pacific Islander, White, or Multiple
- Geographic Region Subgroups:
 - Geographic region: Europe, non-Europe
 - Geographic region: America, Asia, Europe
 - Geographic region: North America (US including Puerto Rico if any, Canada), rest of the World
 - Geographic region: US (including Puerto Rico if any), non-US
- Baseline Severity of Disease Subgroups:
 - Baseline CRP categories:
 - ≤3.00 mg/L or >3.00 mg/L

- ≤ 5.00 mg/L or > 5.00 mg/L
 - ≤ 10.00 mg/L or > 10.00 mg/L
 - ≤ 15.00 mg/L or > 15.00 mg/L
- Baseline MRI status:
 - SPARCC SIJ score ≥ 2 or < 2
 - SPARCC Spine score ≥ 2 or < 2
 - ASSpiMRI-Berlin score > 0 or $= 0$
- Other Patient Characteristics Subgroups:
 - Duration of symptom since AxSpA onset category: < 10 years or ≥ 10 years;

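### Does the sparse-data fallback to Fisher's exact test need a stated trigger for an arm with no responders?

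*SAP*

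**What the plan says.** Under SAP Section 6.1.1, the primary method for categorical efficacy variables is logistic regression with treatment, region (Europe or non-Europe) and baseline CRP status, run in PROC LOGISTIC with a Wald test. Two sentences of that paragraph matter here. The required output is: "The odds ratio and 95% CIs will be reported; treatment difference and 95% CI will also be reported". The fallback to Fisher's exact test applies "In the case when logistic regression model does not produce statistical results due to sparse data".

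ASDAS inactive disease is one of the eight major secondary outcomes in the graphical procedure (SAP Section 6.5), and the abbreviations to Figure RHBV.6.3 place it in Tier 2. SAP Table RHBV.6.5 gives its gated method: "Major secondary efficacy analysis is logistic regression analysis with NRI for ITT Population comparing IXE80Q2W & IXE80Q4W vs. placebo at Week 16". The same table plans Fisher's exact test with NRI for this endpoint as another secondary analysis at Week 16 and at all other Period 2 visits.

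Protocol Section 9.2.1 has Fisher's test only as a secondary analysis. Protocol Section 9.2 leaves the detail to the SAP: "Complete details of the planned analyses will be documented in the SAP".

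**The concern.** Nothing in either document says what counts as failing to produce results. There is no zero-cell rule, separation criterion or minimum count, and it is not stated whether the switch covers the whole model or a single comparison. Other conditional rules in the SAP look firmer: the repeated-measures models change covariance structure on "If the unstructured covariance matrix results in a lack of convergence", and subgroup tests are dropped "If any group within the subgroup (for example, yes, no) is <10% of the total population".

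When one compared arm has no responders, the treatment log odds ratio has no finite maximum likelihood estimate. An iterative fit may still stop and print a large coefficient, a much larger standard error and a p-value near 1. Taken literally, that is a result, and it could enter the graph in place of a small Fisher p-value. ASDAS inactive disease is the gated endpoint most exposed, because it is demanding and few placebo patients may reach it. At stake would be a true effect missed in a confirmatory test, and a p-value that depends on where the software stopped.

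**Working it through.** **Inputs.** 80 patients per arm; ASAS40 rates 44% and 16%; two-sided Fisher's exact test at 0.05 (SAP Section 5.3). ASDAS formula and the cut-off of 1.3 (SAP Table RHBV.6.4). Alpha of 0.025 per regimen on entering Tier 1 (SAP Section 6.5, Step 3). The documents give no rate for ASDAS inactive disease, and the within-tier weights are in figures not shown, so the rates and local alphas below are assumptions.

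**The plan's own figure.** Exact Fisher power for 44% against 16% with 80 per arm is 96.7%, in agreement with the stated approximately 96%.

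**How demanding the endpoint is.** The CRP rule is: "If CRP <2 mg/L or below the limit of detection, then use 2 mg/L in the calculation". At that floor the CRP term is 0.579 × ln(3) = 0.6361, which matches the minimum score in the table. The four patient-reported weights sum to 0.121 + 0.110 + 0.073 + 0.058 = 0.362. The weighted mean of those items must therefore be below (1.3 − 0.6361)/0.362 = 1.83 out of 10, so low placebo rates are plausible.

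**What a fit does with 0/80 on placebo.** A hand-coded Newton fit of the four-arm model (not SAS), with 13/80 in each other arm, gives Wald p = 0.64, 0.93 and 0.998 after 8, 12 and 20 iterations. Fisher p = 0.00014. With 1 or 2 placebo responders against 13/80 the fit converges (Wald p = 0.009 both times), so the difficulty is confined to an empty arm.

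**When the readings could give different decisions.** Fisher's test against 0/80 gives p = 0.028 for 6/80, 0.0136 for 7/80 and 0.0065 for 8/80. The thresholds are therefore 6, 7 and 8 responders at local alpha 0.05, 0.025 and 0.0125. To the accuracy shown,

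P(readings differ) = (1 − p0)^80 × P(X ≥ threshold), with X binomial(80, p1).

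At alpha 0.025 (threshold 7):

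| Placebo p0 | Ixekizumab p1 | (1 − p0)^80 | P(X ≥ 7) | Product |
|---|---|---|---|---|
| 1% | 12% | 0.4475 | 0.859 | 38.4% |
| 2% | 15% | 0.1986 | 0.966 | 19.2% |
| 3% | 16% | 0.0874 | 0.980 | 8.6% |
| 5% | 16% | 0.0165 | 0.980 | 1.6% |

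At alpha 0.05 the products are 41.6, 19.6, 8.7 and 1.6%; at 0.0125 they are 33.9, 18.4, 8.3 and 1.6%.

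**These describe a stand-alone test.** ASDAS inactive disease is reached only after ASAS40 is rejected for both regimens and alpha has passed on from Tier 1. A differing decision on the gated claim requires all of that as well, so its probability cannot exceed the figures shown.

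**The primary endpoint.** At the assumed 16% placebo rate, P(0/80) = 0.84^80, about 9 × 10⁻⁷.

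**Type I error.** With Fisher's test used whenever either arm has none or all responding, and the unadjusted Wald test otherwise, the exact size over common rates of 0.5% to 30% is at most 0.049, 0.0232 and 0.0113 at nominal 0.05, 0.025 and 0.0125. The natural reading does not inflate error on that grid.

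**The case for a change.** The strongest case for adding a sentence is that a confirmatory test should not depend on how a programmer interprets a phrase. A separated fit can print an estimate and a p-value, the decision could turn on it, and one line would settle the matter without altering a test, the sample size or alpha.

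The text is indeed silent on the trigger, and that much stands. The harmful reading, however, requires someone to accept as a statistical result a p-value that moves from 0.64 to 0.998 with the iteration count, while unable to report the finite odds ratio and interval that the same paragraph requires. The evidence that software would offer such a value unflagged comes from emulation, not SAS output. Nor do the comparison rules show a stricter standard: the convergence rule also relies on what the software reports, and the 10% rule concerns subgroup size, not responder counts.

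The unit of the switch is the more genuine gap. Suppose only adalimumab were empty, with placebo 3/80 and Q4W 12/80. The Q4W contrast stays estimable, with Wald p = 0.0219 in the emulated fit; Fisher's test gives 0.0271. A whole-model switch would then move Q4W across 0.025. But an empty adalimumab arm has probability 0.9^80 = 0.02% at an assumed 10% rate. The fallback is worded for the model, so a per-comparison rule would be a new choice, and SAP Version 3 was already approved after unblinding.

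**Conclusion.** No change is needed. This is missing detail inside a fallback that already names the situation, the failure and the replacement test; an analyst who has to report a finite odds ratio and interval is led to Fisher's test when a compared arm is empty. The listed revisions since SAP Version 2 do not mention Section 6.1.1, so on that log the choice of test predates unblinding.

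On the natural reading nothing changes. On the literal reading the difference matters only at placebo rates of about 3% or below. It errs only towards missing a claim, and it leaves ASAS40, the sample size, power and alpha untouched. Fisher's p-value for ASDAS inactive disease is planned under either reading. These sizes rest on assumed response rates, assumed local alphas and 80 patients per arm. If an arm with no responders did occur, it is enough for the study report to state that the Fisher p-value entered the graphical procedure under the existing fallback, and whether the switch was made per comparison.
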